9.2.3. Dilated Indirect Ophthalmoscopy

The investigator will assess the status (Normal, Abnormal – Clinically Significant, Abnormal – Not Clinically Significant) of the vitreous, macula, retina, optic nerve, choroid, and retinal periphery. On Day 1, this assessment will be performed pre- and post-administration of study treatment. Post-administration of study treatment, the investigator will assess the adequacy of the central retinal artery perfusion and indicate the presence of any complications.

Data from the indirect ophthalmoscopy examination will be presented in a listing.

9.2.4. Slit Lamp Examination

The investigator will assess any changes in lens or cataract status and the status (Normal, Abnormal – Clinically Significant, Abnormal – Not Clinically Significant) of the conjunctiva, cornea, iris, anterior chamber, and posterior chamber.

A summary table presenting the number and percentage of eyes with a change in lens/cataract status since screening or a worsening of an existing cataract since the previous visit will be presented by baseline lens status, treatment group for the Safety population with a phakic or pseudophakic lens status at study entry for the given eye.

Data from the slit lamp examination will be presented in a listing.

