8.2. Subject Exclusion Criteria

- 1. Allergy to fluocinolone acetonide or any component of the FAI insert
- 2. Ocular malignancy in either eye, including choroidal melanoma
- 3. Uveitis with infectious etiology
- 4. Current viral diseases of the cornea and conjunctiva including epithelial herpes simplex keratitis (dendritic keratitis), vaccinia, and varicella
- 5. Current mycobacterial infections of the eye or fungal diseases of ocular structures
- 6. Subjects who yield, during screening, a confirmed positive test for human immune deficiency virus (HIV) or syphilis
- 7. Systemic infection within 30 days prior to study Day 1
- 8. Peripheral retinal detachment in area of insertion
- 9. Elevated intraocular pressure (IOP) > 21 mmHg, or chronic hypotony < 6 mmHg
- 10. Concurrent therapy at Screening with IOP-lowering pharmacologic agent in the study eye
- 11. Current diagnosis of any form of glaucoma or ocular hypertension in study eye at Screening, unless study eye has been previously treated with an incisional surgery procedure that has resulted in stable IOP in the normal range (10-21 mmHg)
- 12. Known history of clinically significant IOP elevation in response to steroid treatment in either eye, unless study eye has been previously treated with an incisional surgery procedure that has resulted in stable IOP in the normal range (10-21 mmHg)
- 13. Ocular surgery or capsulotomy performed on the study eye within 30 days prior to study Day 1
- 14. Intravitreal treatment of study eye: with FAI insert within 36 months prior to study Day 1; with Retisert within 30 months prior to study Day 1; with Ozurdex within 90 days prior to study Day 1; or with Triesence or Trivaris within 30 days prior to study Day 1
- 15. Peri-ocular or subtenon steroid treatment of study eye within 30 days prior to study Day 1
- 16. Treatment with an investigational drug or device within 30 days prior to study Day 1, except the FAI insert within this protocol

- 17. Pregnant or nursing females; females of childbearing potential who are unwilling or unable to use an acceptable method of contraception as outlined in this protocol from at least 14 days prior to study Day 1 until the Month 12 Visit
- 18. Any condition which, in the judgment of the Investigator, could make the subject inappropriate for entry into this study

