9.5. Study Schedule

See Table 2 for the schedule of visits and assessments. The screening visit and Day 1 (administration of study treatment) are to be within a 60-day period. The windows for the follow-up visits are Day 7: +/- 3 days; Day 28: +/- 14 days; Month 3: +/- 21 days; Month 12: +/- 28 days.

9.6. Screening, Day -60 to Day 0

All study data will be collected for all subject eyes, at screening and subsequent study visits.

After obtaining informed consent, the following assessments will be performed:

- Demographic information, medical history and ophthalmic history including a history of the subject's uveitis and its management over the previous 12 months
- Height, weight and vital signs (includes systolic/diastolic blood pressure and pulse rate after subject is in the sitting position for at least 5 minutes)
- HIV and syphilis serology testing
- Ophthalmic exam, including: BCVA, IOP (recorded as the mean of three measurements), dilated indirect ophthalmoscopy and anterior, posterior and intermediate slit lamp examinations

- Visual field
- Collect urine for urine pregnancy test (females of childbearing potential)
- Concomitant medications
- Verification that the subject satisfies all inclusion and exclusion criteria. Investigators should not continue screening any subject who does not meet the screening eligibility requirements

When screening assessments have been completed, the Investigator should schedule the subject to return for the Day 1 visit.

9.7. **Procedures on Day of Treatment (Day 1)**

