9.7.2. Data Collection Prior to Intravitreal Administration of FAI Insert

- Vital signs (blood pressure and pulse rate after subject is in the sitting position for at least 5 minutes)
- Ophthalmic exam, including: BCVA, IOP (recorded as the mean of three measurements), dilated indirect ophthalmoscopy and anterior, posterior and intermediate slit lamp examinations
- Urine Pregnancy test
- Concomitant medications
- Verification that the subject/study eye satisfies all other inclusion and exclusion criteria

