9.15.1. Slit Lamp Examination

Slit lamp examination should be performed using the Investigator's standard procedure. This procedure should be the same for all subjects examined at the site and use the same equipment. Observations should be made to indicate the absence or presence of findings for conjunctiva, cornea, iris, and anterior and posterior chambers. All findings are to be documented in the source documentation and the appropriate eCRF.

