When count data are presented, the percentage will be suppressed when the count is zero in order to draw attention to the non-zero counts. A row denoted "Missing" will be included in count tabulations where specified on the shells to account for dropouts and missing values. For by treatment summaries, the denominator for percentages will be the number of eyes in each category in that treatment within the analysis population of interest, unless otherwise specified. For summaries for all subjects for data summarized at the subject level, the denominator for percentages will be the number of subjects who have at least one eye within the analysis population of interest, unless otherwise specified.

Unless otherwise specified, baseline will be defined as the last non-missing evaluation prior to or on the date of treatment injection (Day 1). The study day will be calculated as assessment date – date of treatment injection (Day 1) + 1. Study day for non-ocular events and assessments will be determined using the date of treatment in the first treated study eye. Study day for ocular assessments for the first treated eye will be determined using the date of treatment in the first treated study eye. If the second eye is also treated, study day for the ocular assessments in that eye will be based on the date of treatment in that eye. If the second eye is not treated, study day for ocular assessments in that eye will be based on the date of treatment in the treated study eye.

For all utilization and safety analyses, analysis visit windows will be used for assigning assessments to an analysis visit, as follows:

Scheduled Visit	Target Day	Visit Window (Days)		
Screening	-60 to 0	Not applicable		

Day 1	1	Not applicable
Day 7	7	4 to 10
Day 28	28	14 to 42
Month 3	90	69 to 111
Month 12	360	332 to 388

Only those assessments which are assigned to an analysis visit will be included in the summary tables and figures which are presented by visit. If there are multiple assessments assigned to the same visit window, the observation to be used for analysis will be determined as follows:

If there is only one observation falling into a defined visit window, then that observation will be flagged for inclusion in by-visit analyses.

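### SAP 9.2.4 measures new lens/cataract status change from Screening rather than from the Day 1 pre-injection examination, so the table can mix pre- and post-injection changes

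*SAP*

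**What the plan says.** SAP 9.2.4 plans one summary table from the slit lamp examination: the number and percentage of eyes with a "change in lens/cataract status since screening or a worsening of an existing cataract since the previous visit". It has two limbs with different references. A change in lens or cataract status is measured from Screening; worsening of an existing cataract is measured from the previous visit. The table is to be "presented by baseline lens status, treatment group for the Safety population with a phakic or pseudophakic lens status at study entry". Study entry is not separately defined.

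Protocol 9.5 sets the interval: "The screening visit and Day 1 (administration of study treatment) are to be within a 60-day period". Protocol 9.7.2, headed "Data Collection Prior to Intravitreal Administration of FAI Insert", includes "dilated indirect ophthalmoscopy and anterior, posterior and intermediate slit lamp examinations". Each eye should therefore have a second slit lamp examination after Screening and before injection.

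The default rule in SAP section 4 is that "baseline will be defined as the last non-missing evaluation prior to or on the date of treatment injection (Day 1"), unless another definition is specified. Changes in BCVA, IOP and visual field (SAP 9.2.1, 9.2.2 and 9.3) are all measured from baseline. The IOP threshold counts in SAP 9.2.2 are also restricted to assessments after administration; the lens table carries no such restriction.

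**The concern.** Development or worsening of cataract is listed as a safety outcome of the insert (Protocol 13.3; SAP 3.2). Protocol 5.2.3 names cataract and elevated IOP as the adverse events expected most often. The SAP 9.2.4 table is the planned examination-based summary of lens change; the remaining slit lamp data are only listed.

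If a lens status change occurs between Screening and Day 1, it is present at the pre-injection examination and cannot be due to the insert or the procedure. Under the Screening reference it is nevertheless a change at every later visit. The two limbs are joined into one count, so that count inherits the Screening reference even where the worsening limb is sound.

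The grouping and the outcome can also rest on different visits. Exclusion 13 bars only "Ocular surgery or capsulotomy performed on the study eye within 30 days prior to study Day 1". An eye that was phakic at a Screening 60 days before Day 1 and had lens surgery by about 31 days before Day 1 stays eligible. By the default rule it falls in the pseudophakic baseline row, yet it counts as changed since Screening. The example is narrow. Exclusion 13 does not address a cataract that appears without surgery, and Protocol 5.1 lists cataract among the causes of vision loss in posterior uveitis.

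**Working it through.** The plan states no figure that depends on this reference visit, so there is nothing to reproduce. The check is how much of the status-change interval lies before injection.

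**Inputs**
- Gap from Screening to Day 1: at most 60 days (Protocol 9.5). Gaps of 14 and 30 days are added as illustrations.
- Target study days 7, 28, 90 and 360 (SAP section 4, visit windows).
- Study day is the assessment date minus the injection date plus 1 (SAP section 4), so days since injection = study day − 1.
- Planned arms: 20 Mk II eyes and 10 Mk I eyes.

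**Share of the interval before injection** = gap / (gap + study day − 1)

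| Gap (days) | Day 7 | Day 28 | Month 3 (Day 90) | Month 12 (Day 360) |
|---|---|---|---|---|
| 14 | 14/20 = 70% | 14/41 = 34% | 14/103 = 14% | 14/373 = 4% |
| 30 | 30/36 = 83% | 30/57 = 53% | 30/119 = 25% | 30/389 = 8% |
| 60 | 60/66 = 91% | 60/87 = 69% | 60/149 = 40% | 60/419 = 14% |

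These are shares of time, not of events. With the Day 1 pre-injection examination as reference, the share is 0% at every visit.

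**Weight of one eye.** 1/20 = 5 percentage points for Mk II and 1/10 = 10 points for Mk I. Within a lens-status row the denominator is smaller, so one eye weighs more.

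**How many eyes.** The documents give no rate of lens change before treatment. Assume an annual rate r for each eye, a 60-day gap, and all 30 eyes at risk and independent. Then p = 1 − (1 − r)^(60/365.25), the expected number is 30p, and the chance of at least one such eye is 1 − (1 − p)^30.

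| Assumed r | p | Expected eyes of 30 | Chance of at least one |
|---|---|---|---|
| 5% | 0.0084 | 0.25 | 22.3% |
| 10% | 0.0172 | 0.51 | 40.5% |
| 20% | 0.0360 | 1.08 | 66.7% |

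For each assumed rate these are upper-end illustrations: every eye is given the maximum gap, and all 30 are treated as at risk.

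**The worsening limb.** At Day 7 the previous scheduled visit is Day 1, so this limb already has a pre-injection reference close to treatment. Pre-injection worsening enters only if Day 1 records are themselves tabulated, which SAP 9.2.4 leaves open.

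**The case against.** The strongest reply is that this is a supporting table and that cataract is mainly handled elsewhere. Cataract TEAEs have their own summary (SAP 9.1.8). Ocular TEAEs are counted for a treated eye only from that eye's injection date (SAP 9.1.1), and cataract surgeries are analysed separately (SAP 7.2.2). All slit lamp data are listed, so a change already present on Day 1 can be traced. This stands and limits the consequence. It does not give a reason for the Screening reference, and the examination-based table and the TEAE summary could disagree on the same eye without explanation.

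A reader might also infer more than the documents support:

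- *That pre-treatment changes are reported as treatment effects.* SAP 9.2.4 labels the count by its Screening reference and does not call it treatment-emergent. What is supported is that the table can mix the two periods.
- *That the whole table is measured from Screening.* Only the status-change limb is.
- *That the SAP breaks its own baseline rule.* The rule allows exceptions that are specified, and 9.2.4 specifies one. The point is that the exception is unexplained and sits beside a grouping by baseline lens status.
- *That a second eye may have a gap of 69 days (60 + 9).* This assumes that the second eye, randomized as late as the first eye's Day 10, keeps the first eye's Screening visit. Protocol 9.5 requires Screening and Day 1 to fall within 60 days, and neither document says that a second eye may exceed this.
- *That lens status is not secured on Day 1.* Protocol 9.15.1 asks for the "absence or presence of findings for conjunctiva, cornea, iris, and anterior and posterior chambers" and omits the lens. But SAP 9.2.4 has the investigator assess lens and cataract changes, and SAP 6.2 summarizes lens status. The eCRF is not among the documents, so a data gap is conjecture.

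**Conclusion.** The point holds for the status-change limb. As written, a lens or cataract status change that arose after Screening and before injection is counted at the Day 7 and Month 12 analyses, although a pre-injection examination that could exclude it is scheduled.

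The consequence is limited. It concerns absolute descriptive incidence, mainly at Day 7, where up to 91% of the interval can precede injection; by Month 12 this is at most about 14% at the target day. Under the assumed rates, about 0.25 to 1.08 of 30 eyes would be affected, but the true rate is unknown. A reader might infer that the inserter comparison is biased. The documents do not support that: eyes are randomized and both arms receive the same insert, so no systematic difference is expected, although a single eye is visible in arms this small. The Mk II success criterion rests on ease-of-use ratings and does not use this table. This is a minor but specific correction to the SAP.

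**What to change.** In SAP 9.2.4:

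1. Measure new lens/cataract status change from each eye's own Day 1 pre-injection slit lamp examination, using Screening only if the Day 1 examination is missing.
2. Limit both limbs of the table to post-administration visits, as SAP 9.2.2 does for its IOP threshold counts.
3. Leave the worsening limb referenced to the previous visit. Moving it to Day 1 would turn visit-to-visit worsening into cumulative worsening, which this problem does not require.

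No new examination is needed. The cost is a small change to SAP and programming wording. If the eCRF asks the investigator about change since Screening in those terms, the form or its derivation would need the same edit. Adding the lens to the structures listed in Protocol 9.15.1 would align it with SAP 9.2.4, but this is optional.

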9.2.5. Vitreous Haze and Anterior Chamber Cells

Indirect ophthalmoscopy will be performed for each eye with pupil dilation. The following scale (Nussenblatt 1985) will be used to define the extent of vitreous haze:

Grade	Description
Absent	Clear view of optic disc, retinal vessels and nerve fiber layer
Trace	Slight blurring of optic disc margin and of normal striations and reflex of nerve fiber layer
1+	Mild blurring of optic disc margin and slight loss of retinal vessel definition
2+	Moderate blurring of optic disc margin and loss of retinal vessel definition
3+	Optic nerve head and large vessels visible but borders quite (very) blurry
4+	Optic nerve head obscured

Anterior chamber cells will be measured using a Haag/Streit or similar slit lamp at high magnification (1.6 X) 1-mm beam. Assessment will be made using the following scale (Jabs 2005).

Field size: 1 mm by 1 mm slit beam

Grade	Description
0	<1 cells/hpf
0.5+	1-5 cells/hpf
1+	6-15 cells/hpf
2+	16-25 cells/hpf
3+	26-50 cells/hpf
4+	>50 cells/hpf

Frequency distributions of the vitreous haze and anterior chamber cells grading at each scheduled visit will be summarized in a table by treatment group in the Safety population.

All vitreous haze and anterior chamber cell data will be presented in a listing.

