9.10. Unscheduled Follow-up Visits

Additional examinations may be conducted as necessary to ensure the safety and well-being of subjects during the study period. Electronic case report forms (eCRFs) should be completed for each unscheduled visit or test that the subject completes.

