11.1.3. Protocol-Defined Ocular Adverse Events

The following ocular events must be reported as AEs during this trial:

- decrease in visual acuity of ≥ 15 letters, compared to the most recent previous measurement of visual acuity
- moderate or severe (grade 3 or 4) ocular findings compared to the last ophthalmic examination
- worsening of ≥ 2 steps in anterior chamber cell count or vitreous haze, compared to the last ophthalmic examination
- increase in IOP of \geq 10 mmHg at two visits at least 1 week apart or an increase in IOP to \geq 25 mmHg

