11.4.3. Other Safety Considerations

Any significant changes noted during interim/final examinations, procedures or any other potential safety assessment should also be recorded on the appropriate AE or SAE eCRF.

For additional information, Investigators should contact:

PPD Medical Support Center

[contact]Telefax:[name]

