7.1.2 Concomitant Medications

Concomitant medications are defined as those medications which are taken on or after the initiation of study treatment (Day 1). This includes medications which start prior to Day 1 but continue while the subject is on treatment.

Concomitant non-ocular medication will be summarized by treatment group for ATC level 1 term, ATC level 2 term and preferred term for the Safety population. The concomitant nonocular medication data will be also summarized for all subjects at the subject level. Summaries by treatment group will be based on the number of treated eyes; therefore a subject who has both eyes treated will be counted more than once, "repeating" and counting the non-ocular medication once for each treated eye. Percentages for the by treatment summaries will be based on the number of treated eyes and percentages for the total subjects summary will be based on the number of subjects who have at least one eye treated.

Concomitant ocular medication will be summarized by treatment group and for all treated eyes for each drug class and preferred term for the Safety population. Percentages will be based on the number of treated eyes.

An additional summary of concomitant medication for each of the specified reasons for medication (recurrence of uveitis, treatment emergent AE, increased IOP, cataract, other) will be reported as well.

7.1.3 **IOP Lowering Medications**

The number and percentage of eyes requiring IOP lowering medication to control elevated IOP will be summarized by treatment group and for all treated eyes. Any systemic medications will be summarized as received in both eyes. IOP lowering medications will be identified as those medications with a reason for medication of "Increased IOP". Incidence will be summarized through 12 months and for 3 month time intervals through 12 months.

The number of medications (one, two, \geq three) required to achieve adequate IOP control will also be included in the summary. IOP medications will be counted at the "ingredient" level. For example, if the subject is receiving COSOPT (which contains two ingredients TIMOLOL MALEATE and DORZOLAMIDE HYDROCHLORIDE) and TIMOLOL MALEATE at the same time, the subject will be included in analysis as receiving two medications.

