7.2. Ocular Surgeries

All ocular surgeries during a subject's participation in the study will be recorded on the eCRF.

A summary of surgery/procedure for each of the specified reasons (recurrence of uveitis, treatment emergent AE, increased IOP, cataract, other) will be reported. Summaries will be provided by treatment group and for all treated eyes for the Safety population.

Ocular surgery data, including details on the procedure, eye, start date, and reason for the surgery, will be presented in a listing for the Safety population.

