The summary of TEAEs will be presented in descending order from the SOC with the highest subject incidence to the SOC with the lowest subject incidence. If the incidence for any two or more SOC is equal, the SOC will be presented in alphabetical order. Within each SOC, the PTs will be presented in alphabetical order.

A separate summary of protocol defined ocular TEAEs, overall and by criteria, will be provided. This summary will include the following ocular events, as reported on the AE eCRF page:

- decrease in visual acuity of \geq 15 letters, compared to the most recent previous measurement of visual acuity
- moderate or severe (grade 3 or 4) ocular findings compared to the last ophthalmic examination
- worsening of ≥ 2 steps in anterior chamber cell count or vitreous haze, compared to the last ophthalmic examination
- increase in IOP of \geq 10 mmHg at two visits at least 1 week apart or an increase in IOP to \geq 25 mmHg

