9.1.4. Serious Adverse Events

Serious treatment-emergent adverse events (SAEs) as below will be presented in a table by incidence of occurrence by treatment group.

- Results in death
- Is life-threatening
- Requires in-patient hospitalization or prolongs existing hospitalization
- Results in persistent or significant disability / incapacity
- Is a congenital anomaly / birth defect
- Is a medically important event or reaction

The SAE data will be categorized and presented by SOC and PT in a manner similar to that described in Section 9.1.1 and by severity as described in Section 9.1.3.

A separate summary of protocol defined SAEs, overall and by criteria, will be provided. This summary will include the following sight-threatening ocular events, as reported on the AE/SAE eCRF page:

- An AE which causes a decrease in visual acuity of ≥ 30 letters, compared to the most recent previous measurement of visual acuity, lasting more than 1 hour
- An AE which causes a decrease in visual acuity to light perception or worse, lasting more than 1 hour
- An AE which requires surgical intervention (e.g., conventional surgery, vitreous tap or biopsy with intravitreal injection of anti-infective, or laser or retinal cryopexy with gas) to prevent permanent loss of sight
- An AE which is associated with severe intraocular inflammation (i.e., 4.0 anterior chamber cell score, 4+ flare or 4+ vitritis)
- Two consecutive IOP measurements of 30 mmHg or higher taken at least 72 hours apart when a subject is already being treated with two glaucoma medications
- An IOP < 6 mmHg requiring medical intervention
- An AE which in the opinion of the Investigator requires medical or surgical intervention to prevent permanent loss of sight

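### SAP 9.2.5 tabulates vitreous haze and anterior chamber cell grades only as marginal frequencies by visit, so the tables generally do not give the number of eyes worse than their own baseline

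*SAP*

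**What the plan says.** SAP 9.2.5 states the display: "Frequency distributions of the vitreous haze and anterior chamber cells grading at each scheduled visit will be summarized in a table by treatment group", for the Safety population, with all grades in a listing. Neither document plans a shift table, a change from baseline or a worst post-baseline summary for these two grades. Ophthalmoscopy findings are listed only (SAP 9.2.3), and the slit lamp table covers only lens and cataract status (SAP 9.2.4).

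Worsening can reach a table by other routes:

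- Protocol 11.1.3 requires an AE report for worsening of at least 2 "steps in anterior chamber cell count or vitreous haze, compared to the last ophthalmic examination", and for grade 3 or 4 ocular findings. SAP 9.1.1 tabulates these events, but from reports and not from the grades: "This summary will include the following ocular events, as reported on the AE eCRF page".
- SAP 9.1.4 tabulates protocol-defined SAEs, among them "An AE which is associated with severe intraocular inflammation".
- Protocol 11.4.3 says that significant changes at examinations "should also be recorded on the appropriate AE or SAE eCRF". Reported events then enter the general TEAE tables.
- SAP 7.1.2 and 7.2 summarise concomitant medication and ocular surgery by reason, and recurrence of uveitis is one of the reasons.

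For visits outside the schedule, Protocol 9.10 says that eCRFs "should be completed for each unscheduled visit or test that the subject completes".

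**The concern.** A frequency table at each visit describes the group and does not follow the eye. If one eye goes from Absent to Trace and another from Trace to Absent, the table does not change. The AE route does not fully make up for this, because its step criterion compares with the last examination. An eye can rise one step at a time and never meet it.

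At stake is a descriptive number: how many eyes have more inflammation than before the injection. It bears mainly on the secondary objective, safety of the insert over 12 months. The SAP gives this kind of within-eye summary for BCVA (9.2.1), IOP (9.2.2) and visual field mean deviation (9.3), but not for the two direct grades of intraocular inflammation in a uveitis trial.

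**Working it through.** **Inputs.** Six ordered grades per measure (SAP 9.2.5: Absent, Trace, 1+ to 4+ for haze; 0, 0.5+, 1+ to 4+ for cells). Scheduled examinations at Day 1, Day 7, Day 28, Month 3 and Month 12. AE criteria from Protocol 11.1.3. Planned group sizes of 20 and 10 eyes. Each listed category is counted as one step, which is an assumption because the documents do not define a step.

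**Step 1. The plan's own figures.** The plan gives none on this point. Its sample-size figures are exact 95% intervals for the primary endpoint. They reproduce (10/20: 27.20% to 72.80%; 5/10: 18.71% to 81.29%) but play no part here.

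**Step 2. What marginal frequencies can show.** With the same eyes at both visits, the smallest number of worsened eyes is the largest value, over all grades g, of (eyes above g at the visit) − (eyes above g at baseline), or 0 if that is negative. The number cannot exceed the eyes above the lowest grade at the visit. The documents give no baseline grade mix, so the frequencies below (Absent/Trace/1+/2+) are assumed for illustration.

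| Baseline | Follow-up | Fewest worse | Most worse |
|---|---|---|---|
| 8/6/4/2 (n = 20) | 8/6/4/2 | 0 | 6 + 4 + 2 = 12 |
| 4/3/2/1 (n = 10) | 4/3/2/1 | 0 | 3 + 2 + 1 = 6 |
| 8/6/4/2 (n = 20) | 6/6/5/3 | 14 − 12 = 2 | 6 + 5 + 3 = 14 |
| 20/0/0/0 (n = 20) | 15/5/0/0 | 5 | 5 |

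The maximum of 12 in the first row needs only one-step rises: 6 eyes Absent to Trace, 4 Trace to 1+, 2 from 1+ to 2+, with 6 others (2 each from Trace, 1+ and 2+) falling to Absent. The third row shows a net shift giving a lower bound. The last row shows that the table is exact when every eye starts at the lowest grade.

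**Step 3. Which worsenings meet no AE grade trigger.** Six grades give 6 × 5 / 2 = 15 ways to be worse than baseline. Enumerate all 6^5 = 7,776 sequences over the five examinations. Drop any with a rise of 2 or more steps between consecutive examinations, or with a post-baseline grade of 3+ or 4+. Among the four grades up to 2+, a rise of k steps can occur in 4 − k ways, so the surviving baseline-to-visit pairs are:

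- Day 7 (at most 1 step): 3 of 15.
- Day 28 (at most 2 steps): 3 + 2 = 5 of 15.
- Month 3 (at most 3 steps): 3 + 2 + 1 = 6 of 15.
- Month 12 (still at most 3 steps): 6 of 15.

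Example: Absent, Trace, 1+, 2+ at Day 1, Day 7, Day 28 and Month 3 is 3 steps worse than baseline with no trigger.

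**Step 4. Sensitivity to the grade 3 or 4 criterion.** Protocol 11.1.3 does not name the scales to which that criterion applies. If only 4+ triggers, through the severe-inflammation SAE, five grades remain. The counts become 4, 4 + 3 = 7, 4 + 3 + 2 = 9 and 4 + 3 + 2 + 1 = 10 of 15, with maximum rises of 1, 2, 3 and 4 steps.

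**Step 5. Unscheduled visits.** SAP 4 uses windows of days 4 to 10, 14 to 42, 69 to 111 and 332 to 388. An unscheduled grade on days 11 to 13, 43 to 68 or 112 to 331 is in no by-visit table. The last gap is 331 − 112 + 1 = 220 days. Inside a window, a scheduled observation displaces an unscheduled one. Such a grade is seen only in the listing unless it was reported as an AE. Steps 3 and 4 assume no extra examination between scheduled visits; each extra one allows a further one-step rise.

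**The case against.** The strongest reply is that little is left once the other routes are counted. The AE definition includes worsening of a pre-existing condition (Protocol 11.1.1 and 11.3), and Protocol 9.11 calls for standard therapy when uveitis worsens or recurs. For the three-step eye in Step 3 to escape every other table, the investigator must neither report nor treat the rise. Nothing in the documents suggests that this is likely. This stands, and it limits the point to unreported, untreated worsening.

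A second reply is that these grades are ordinal, and SAP 4 describes categorical data by counts and percentages, which 9.2.5 does. That is correct but does not settle the matter. The SAP also tabulates categories of change from baseline for BCVA (9.2.1) and IOP (9.2.2), and takes the largest BCVA change at any time point.

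Third, about 30 eyes can be read from a listing. That is true, but the same sample size did not stop the SAP from tabulating change for the other measures.

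Fourth, the decision value is low. The inserter safety evaluation ends at Day 7, when only a one-step rise can miss the trigger on scheduled visits. By Month 12 all treated eyes have the same insert and standard care, so the count cannot separate insert effect from disease course. Nor is it like for like with the protocol-defined AE counts, which use the last examination. All of this stands and sets the weight of the point.

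Fifth, a full shift grid would be excessive: 36 cells × 6 time points or periods × 3 groupings = 648 cells per measure. This stands and shapes the fix.

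**Conclusion.** The point holds as a minor gap in display. The planned tables generally do not give the number of eyes worse than their own baseline for either measure; the marginal frequencies generally give only a lower bound. What can go uncounted is one-step or stepwise worsening that is neither reported as an AE nor treated.

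A reader might infer three stronger things, and the documents support none of them:

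- That such worsening is visible only in listings. A net upward shift shows in the planned table, and treated worsening is summarised under recurrence of uveitis.
- That the gap certainly stops at 2+. This holds only if the grade 3 or 4 criterion is taken to cover these two scales; otherwise it reaches 3+.
- That 3, 5, 6 and 6 of 15 are proportions of eyes. They count possible grade pairs. Neither the baseline grade mix nor the number of unscheduled visits is given, so the number of affected eyes cannot be estimated and may be zero.

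The counts rest on one listed category being one step; if a step means a full grade, fewer moves trigger an AE. The analysis is descriptive, all grades are listed, and the primary endpoint and success rule are unaffected.

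**What to change.** Add to SAP 9.2.5, for each measure, the count and percentage of eyes worse than the pre-injection baseline grade, and of eyes 2 or more steps worse. Give these at each scheduled visit and for the worst post-injection grade through Day 7 and through Month 12, with unscheduled visits included in the worst grade. Present them by inserter and for all treated eyes, derived from the recorded grades, and state that one listed category is one step. Add one shift table per measure of baseline grade by worst grade through Month 12; a grid at every visit is not needed. Keep the AE-based summaries as planned.

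The cost is a few lines of SAP text, a small amount of programming and some sparse cells. No new data are needed.
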